The Safety and Efficacy of Pulsed Field Ablation for Patients with Persistent Atrial Fibrillation Comorbid with HFpEF: a prospective, multicenter cohort study

Protocol Version and Date	V1.0. 20250425
Clinical Research Unit	Affiliated Hospital of Nantong University
Principal Investigator	[name]
Sponsor	Affiliated Hospital of Nantong University

Study plan

Project name	The Safety and Efficacy of Pulsed Field Ablation for Patients with Persistent Atrial Fibrillation Comorbid with HFpEF: a prospective, multicenter cohort study		
Project source	Jiangsu Provincial Research Hospital: YJXYY202204-YSB59		
Main investigator	[name]	Contact	[name]
Funding source	Hospital multi-center clinical research project	Funding received	100,000

Study Protocol Summary

Study number	2025-K119-01
Study name	The Safety and Efficacy of Pulsed Field Ablation for Patients with Persistent Atrial Fibrillation Comorbid with HFpEF: a prospective, multicenter cohort study
Study purpose	To evaluate the difference between pulsed field ablation and medical therapy in patients with persistent atrial fibrillation and HFpEF
Study design	Prospective, multicenter cohort study
Study equipment	Medtronic Pulse Select Pulsed Field Ablation
Sample size	158
Entry criteria	
Inclusion criteria
 
(1) Age 18-80 years;
 
(2) Patients with persistent atrial fibrillation;
 
(3) According to the 2021 European Society of Cardiology (ESC) guidelines for heart failure, heart failure with preserved ejection fraction (HFpEF) is defined as patients with preserved or slightly reduced left ventricular ejection fraction (LVEF) but with diastolic dysfunction. The diagnostic criteria for HFpEF include: symptoms and signs of heart failure; LVEF $\geq 50\%$; and objective evidence of cardiac structural and functional abnormalities consistent with left ventricular diastolic dysfunction or increased left ventricular filling pressure. These can be verified by imaging examinations such as echocardiography and biomarkers such as B-type natriuretic peptide or NT-proBNP. The thresholds for B-type natriuretic peptide or NT-proBNP are: BNP ≥ 35 pg/mL or NT-proBNP ≥ 125 pg/mL for patients with sinus rhythm; BNP ≥ 105 pg/mL or NT-proBNP ≥ 365 pg/mL for patients with atrial fibrillation.
 
(4) Agree to participate in this study and sign the informed consent form. Have clinical compliance to complete the postoperative follow-up required by the protocol.
 
Exclusion criteria
 
(1) Patients with persistent atrial fibrillation lasting for more than 3 years,
 
(2) Patients who had used class I or class III antiarrhythmic drugs, but the use

	
of the above drugs for less than 7 days to convert atrial fibrillation was allowed;
 
(3) Previous left atrial ablation or surgery (including left atrial appendage occlusion);
 
(4) Left atrial diameter > 50 mm;
 
(5) Previous pulmonary vein stenting;
 
(6) Previous pulmonary vein stenosis;
 
(7) Presence of any heart valve prosthesis;
 
(8) Any cardiac surgery, myocardial infarction, percutaneous coronary intervention (PCI)/percutaneous transluminal coronary angioplasty (PTCA) or coronary artery stenting within three months before signing the informed consent;
 
(9) Unstable angina or severe coronary artery stenosis;
 
(10) Primary pulmonary hypertension;
 
(11) Rheumatic heart disease;
 
(12) Thrombocytosis, thrombocytopenia;
 
(13) Any disease that prohibits long-term anticoagulation;
 
(14) Active systemic infection;
 
(15) Atrial fibrillation caused by reversible causes, such as hyperthyroidism;
 
(16) Women known to be pregnant or breastfeeding;
 
(17) Life expectancy of less than one year;
 
(18) Patients with intracardiac thrombus;
 
(19) Patients with known drug or alcohol addiction;
 
(20) Patients who are unwilling or unable to fully comply with the study protocol and complete follow-up;
 
(21) Patients with malignant tumors;
 
(22) Participating in other clinical trials that may interfere with the results.

End point	
Primary endpoint:
 
Change in quality of life at 12 months as measured by the Atrial Fibrillation Quality of Life Survey (AFEQT).
 
Improvement in quality of life from baseline to 12 months after pulsed field ablation procedure or AAD as measured by the Atrial Fibrillation Quality of

	
Life Survey (AFEQT), with values ranging from 20 - 140 (higher scores mean worse outcomes).
 
Secondary End Points
 
(1) The rate of atrial fibrillation-free recurrence during clinical follow-up within 12 months after surgery, that is, the success rate of pulsed field therapy for AF (including atrial tachycardia (AT) lasting more than 30 seconds, atrial flutter (AFL), and AF endpoint events);
 
(2) Complications and adverse events during the pulsed field ablation surgery and during the postoperative follow-up, including readmission, cardiovascular events, cardiovascular death, all-cause death, and also including serious adverse events related to the surgery.
 
(3) Rehospitalization due to heart failure or recurrence of atrial fibrillation 3 months after surgery;
 
(4) The incidence of AT/AF/AFL events 3 months later.;
 
(5) Improvement of cardiac function 6 and 12 months after surgery, including echocardiogram E/e', proBNP, etc.

Statistical analysis
	
OPC was analyzed based on previous clinical research data and used for comparison and evaluation of the main evaluation indicators. According to the current literature on the treatment of drug-refractory atrial fibrillation, the main evaluation indicator comparison target value was 80%.
 
1. Completion status and demographic analysis
 
Summarize the number of enrollments and completions of each center, and list the list of dropouts. Make a detailed list of the size of different data sets in each group, the distribution of cases in each center, the comparison of the total dropout rate, and the reasons for non-completion. Describe, analyze and evaluate the patient's demographic characteristics (age, gender, etc.), relevant medical history, treatment history, etc.
 
2. Safety evaluation
 
List the number and frequency of all adverse events, as well as the incidence of adverse events and serious adverse events. Make a cross-tabulation description of the changes in laboratory indicators before and after. The exact probability

	method was used to compare the two groups of adverse events.
--	--

Flow chart

Name	Screening period		Treatment period		Follow-up period			
	V1	V2	V3	V4	V5	V6	V7	
Visit point								
Visit time	-14d ~ 0d	0 d (Operation)	1-7 d (Before discharge)	1m ± 7d	3m ± 7d	6m ± 7d	12m ± 7d	
Informed consent	X							
General information	X							
Vital signs	X		X	X	X	X	X	
Medical history	X							
Inclusion criteria	X							
Laboratory examination	X		X	X	X		X	
Standard electrocardiogram	X		X	X	X	X	X	
Holter					X	X	X	
AFEQT scale	X			X	X	X	X	
Echocardiogram	X		X	X		X	X	
Medication status	X	X	X	X	X	X	X	
Adverse events	X	X	X	X	X	X	X	

Note: m=month; d=day; h=hour.

(1) **V1 Screening period:** If the patient has undergone relevant examinations before signing the informed consent form and within 14 days before surgery, these data can be collected as data for this clinical trial. Patients do not need to undergo relevant examinations, such as laboratory tests, electrocardiograms, etc.

(2) **General information:** date of birth, gender, height, weight.

(3) **Vital signs:** body temperature, blood pressure, heart rate/pulse.

(4) **Medical history:** including hypertension, diabetes, coronary heart disease, stroke, allergies, surgical history, etc.

5) Pregnancy test: urine/blood pregnancy test (only for premenopausal women, only before surgery).

(6) Laboratory examination (V6 only measures NT-proBNP, and all other visits involving laboratory examinations (such as V1, V3 and V4) must complete all the following examination items):

Routine blood test: red blood cells (RBC), white blood cells (WBC), hemoglobin (Hgb), platelets (PLT); Blood biochemistry: alanine aminotransferase/alanine aminotransferase (ALT), aspartate aminotransferase/aspartate aminotransferase (AST), total bilirubin (TBIL), direct bilirubin (DBIL), blood urea nitrogen/urea (BUN/CREA), creatinine (Cr), uric acid (UA); ESR; Electrolytes: potassium ion (K); Coagulation function: prothrombin time (PT), activated partial thromboplastin time (APTT), fibrinogen (FIB); C β -reactive protein; D-dimer; NT-proBNP; myocardial enzyme spectrum and high-sensitive cardiac troponin T: lactate dehydrogenase (LDH), creatine kinase isoenzyme (CK-MB), and high-sensitive cardiac troponin I (hs-cTnI);

(7) Long-term Holter: Use a single-lead 7-day long-term Holter for monitoring.

(8) Medication status: Record the medication used during the study period (from the signing of the informed consent to the end of the follow-up). Routine fluid preparation (normal saline, glucose solution), intraoperative anesthetics, and intraoperative anticoagulants do not need to be recorded. Medication used for corrective treatment of adverse events also needs to be recorded.

(9) Adverse events: Record clinically significant adverse events of the subject from the signing of the informed consent to the end of the follow-up. Events in which the health status of the subject does not deteriorate seriously due to planned hospitalization for existing diseases or follow-up required by the protocol are not recorded as serious adverse events.

1. Background

Atrial fibrillation (AF) is one of the most common arrhythmias in clinical practice. It is a supraventricular tachyarrhythmia characterized by rapid and disordered atrial electrical activity, with a high disability and mortality rate¹. There are more than 7 million patients with atrial fibrillation in my country. The incidence of atrial fibrillation has increased 20 times compared with ten years ago, and the incidence of atrial fibrillation-related stroke has increased nearly 13 times. Atrial fibrillation not only significantly reduces the patient's cardiac output, leading to heart failure²; It will also increase the risk of left atrial mural thrombus formation, leading to peripheral arterial embolism, especially stroke. Atrial fibrillation (AF) is currently the most common arrhythmia in patients with heart failure (HF)^[1-2]. Studies have shown that atrial fibrillation is more common in patients with ejection fraction preserving heart failure (HFpEF). During the course of HFpEF, atrial dysfunction caused by atrial fibrillation may cause functional mitral regurgitation, further affecting ventricular systolic and diastolic function and accelerating the progression of heart failure. Patients with atrial fibrillation and heart failure have severe symptoms, poor prognosis, and increased hospitalization rates. Studies have reported that the annual incidence of atrial fibrillation in patients with heart failure is about 57%, and the annual incidence of heart failure in patients with atrial fibrillation is about 37%³.

The goal of treating atrial fibrillation combined with heart failure is to alleviate patient symptoms and improve survival rate. The treatment strategies for atrial fibrillation mainly include standardized anticoagulation therapy and catheter ablation. Catheter ablation includes catheter ablation under high-power X-ray guidance, radiofrequency ablation guided by a three-dimensional mapping system, radiofrequency ablation guided by intracardiac ultrasound, high-power short-term radiofrequency ablation, cryoballoon ablation, pulsed field ablation, left atrial appendage occlusion, and "one-stop treatment for atrial fibrillation". Studies have reported that for patients with heart failure and atrial fibrillation, compared with drug treatment, radiofrequency catheter ablation significantly reduces all-cause mortality and heart failure hospitalization rate, and significantly improves cardiac function classification⁴.

Currently, there are two energy sources available for catheter ablation of persistent atrial fibrillation: radiofrequency and cryotherapy. However, both are temperature-dependent. The damage effect depends on the distribution of the temperature field in the target tissue, which is the cause of the therapeutic effect and the additional damage^{5,6}. Currently, the complication rate of radiofrequency or cryocatheter ablation is approximately 2.9% to 10%, of which the incidence of potentially fatal complications is 0.7% to 0.9%. The perioperative mortality rate is 0.05% to 0.55%, and the most common cause is cardiac tamponade^{7,8}. Secondly, under the premise of safety, traditional energy also has certain deficiencies in the transmural properties of myocardial injury.

Pulsed field ablation (PFA) is an emerging ablative energy. The basis for the damage effect of ablation is the voltage difference between the inside and outside of the membrane formed by the high-voltage electric field. This is electric field-dependent, does not generate heat locally, and has strong penetration ability. Under the action of high-voltage electric fields, the damage threshold of different tissues is different. The damage is selective to a certain extent, and it is safer for fragile adjacent tissues such as blood vessels, esophagus, and nerves^{9,10}. Currently, other energy forms used for ablation are not selective for this tissue type. In the global key study, the incidence of unsafe events for the product submitted this time was 0.7%, and no complications such as left atrial-esophageal fistula, pulmonary vein stenosis, myocardial infarction, phrenic nerve palsy, and

coronary spasm occurred. The extremely low incidence of unsafe events demonstrates the excellent safety of the product. Compared with existing technologies, the efficiency of PFA energy may also be improved. PFA delivery is completed in a few milliseconds, which may reduce isolation time and the entire operation time. By reducing the total operation time, the anesthesia time and the time the patient and doctor are exposed to radiation are reduced, which greatly improves the efficiency of the operation^{11,12}. The PulseSelect™ pulsed field ablation system is a ring electrode with a central support. Compared with a point-shaped radiofrequency catheter, it isolates the pulmonary veins by ablating a whole circle of 9 electrodes at the same time, further improving the efficiency of the operation. Due to the uniqueness and safety of its energy, it can significantly reduce postoperative complications and hospitalization time, shorten the patient's recovery period, and reduce the need for secondary treatment, thereby effectively reducing the patient's medical costs and economic burden¹³. The results of the Pulsed AF study also showed that at 6 and 12 months after surgery, the overall quality of life of patients (AFEQT and EQ-5D) increased by 5 points and 0.03 points respectively compared with the baseline level, and the results were statistically significant¹⁴. It can be seen that PFA reduces the overall medical resource investment by reducing the re-ablation rate and cardiovascular events.

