2.1 Research objectives

This study aims to evaluate the mid- and long-term clinical efficacy and safety of pulsed field ablation in the treatment of patients with persistent atrial fibrillation and HFpEF by recording and analyzing the differences between the effects of pulsed field ablation and drug therapy in patients with persistent atrial fibrillation and HFpEF. At the same time, the risk factors affecting the outcome of atrial fibrillation ablation, postoperative recurrence, and improvement of cardiac function were analyzed to better guide the application of pulsed field catheter ablation in persistent atrial fibrillation and HFpEF, and also to provide some theoretical basis and clinical evidence for the treatment strategy of patients with atrial fibrillation and HFpEF.

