2.2 Research content

This study is a prospective, multicenter cohort study.

- (1) To observe the perioperative safety of pulsed field catheter ablation for patients with persistent atrial fibrillation and HFpEF;
- (2) To observe the improvement of cardiac function, the treatment effect and recurrence rate of atrial fibrillation in the pulsed field ablation group compared with the drug treatment group 1 month, 3 months, 6 months and 12 months after surgery;
- (3) To study the treatment strategy during the pulsed field ablation procedure, such as the correlation between ablation time, ablation site and the recurrence of atrial fibrillation and cardiac function after surgery, so as to guide better cryoablation strategies.

3. Study population

This study selected patients with persistent AF and HFpEF and divided them into a drug group (treated with class I or class III antiarrhythmic drugs) and a surgical group (Medtronic Pulse Select pulsed field ablation).

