The following information should be collected/completed at the $6m \pm 15d$ follow-up after surgery:

- ◆ Vital signs
- ◆ Standard electrocardiogram
- ◆ Holter
- ◆ AFEQT quality of life score for patients with atrial fibrillation
- ◆ Cardiac ultrasound
- ◆ Medication status
- ◆ Adverse events & serious adverse events

(7) V8 12 months post-surgery

The following information should be collected/completed at the $12m \pm 15d$ follow-up after surgery:

- ◆ Vital signs
- ◆ Laboratory tests
- ◆ Standard electrocardiogram
- ◆ Holter
- ◆ AFEQT quality of life score for patients with atrial fibrillation
- ◆ Cardiac ultrasound

- ◆ Medication status
- ◆ Adverse events & serious adverse events

Note: Medication status: Record the medication status during the study period (from signing the informed consent to the end of follow-up). Routine solution preparation (normal saline, glucose solution), intraoperative anesthetics, and intraoperative anticoagulants do not need to be recorded. Drugs used for corrective treatment of adverse events also need to be recorded.

Adverse events: Record clinically significant adverse events of the subjects from signing the informed consent to the end of follow-up. Events in which the health status of the subjects does not deteriorate seriously due to planned hospitalization for existing diseases or follow-up required by the protocol are not recorded as serious adverse events.

5. End point

5.1. Primary endpoint:

Change in quality of life at 12 months as measured by the Atrial Fibrillation Quality of Life Survey (AFEQT). Improvement in quality of life from baseline to 12 months after pulsed field ablation procedure or AAD as measured by the Atrial Fibrillation Quality of Life Survey (AFEQT), with values ranging from 20 - 140 (higher scores mean worse outcomes).

5.2 Secondary endpoint:

- (1) The rate of atrial fibrillation-free recurrence during clinical follow-up within 12 months after surgery, that is, the success rate of pulsed field therapy for AF (including atrial tachycardia (AT) lasting more than 30 seconds, atrial flutter (AFL), and AF endpoint events);
- (2) Complications and adverse events during the pulsed field ablation surgery and during the postoperative follow-up, including readmission, cardiovascular events, cardiovascular death, all-cause death, and also including serious adverse events related to the surgery.
- (3) Rehospitalization due to heart failure or recurrence of atrial fibrillation 3 months after surgery;

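### The Summary judges the main indicator against an 80% external target that is undefined for the continuous AFEQT primary endpoint and contradicts the two-group design and sample size

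*Protocol*

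**What the plan says.** The Statistical analysis row of the Study Protocol Summary opens with a benchmark, called an OPC, derived from previous clinical research and "used for comparison and evaluation of the main evaluation indicators". It then gives the value: "According to the current literature on the treatment of drug-refractory atrial fibrillation, the main evaluation indicator comparison target value was 80" per cent. The protocol does not expand OPC; I read it as an objective performance criterion, that is, a fixed external target. It does not define the main evaluation indicator either.

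The rest of the protocol describes something else:

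- Primary endpoint (Summary and section 5.1): "Improvement in quality of life from baseline to 12 months after pulsed field ablation procedure or AAD", measured by AFEQT. No responder threshold is attached.
- Study purpose (Summary): "To evaluate the difference between pulsed field ablation and medical therapy in patients with persistent atrial fibrillation and HFpEF".
- Objective (section 2.1): "analyzing the differences between the effects of pulsed field ablation and drug therapy in patients with persistent atrial fibrillation and HFpEF".
- Groups (section 3): patients are selected and the study "divided them into a drug group (treated with class I or class III antiarrhythmic drugs) and a surgical group" treated with PFA.
- Sample size (section 3.1): a two-sample t-test of mean AFEQT, null difference zero against a two-sided alternative, alpha 0.05.

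One listed efficacy endpoint is naturally a percentage. Secondary endpoint (1), 12-month freedom from recurrence, is glossed as "that is, the success rate of pulsed field therapy for AF".

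**The concern.** A target of 80% needs a proportion to be compared with it. A change in AFEQT score is not a proportion, and the protocol gives no rule for turning it into one. Taken literally, the Summary's criterion for the main indicator cannot be applied to the endpoint that the protocol calls primary.

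The kind of comparison is also wrong for this design. A fixed external target judges one arm against the literature and does not use the drug group. The study is set up and sized to compare two concurrent groups.

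At stake is which result decides the main conclusion. With both criteria in the text, success could be claimed because PFA beats drug therapy on AFEQT, or because some PFA rate reaches 80%. That choice should be closed before results are known.

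**Working it through.** **Step 1. Set the two criteria side by side.**

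| Feature | Summary, Statistical analysis row | Sections 2.1, 3, 3.1 and 5.1 |
|---|---|---|
| Indicator | main evaluation indicator, undefined | change in AFEQT to 12 months (5.1) |
| Type of quantity | percentage | continuous score |
| Comparator | fixed target from literature | concurrent drug group |
| Null hypothesis | none stated; target 80% | difference in means = 0, two-sided |
| Source population | drug-refractory AF | prior class I/III drug users excluded, apart from under 7 days' use for conversion (exclusion 2) |

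The two columns do not agree on any row.

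**Step 2. Reproduce the sample size and see whether 80% enters it.** Inputs from section 3.1: means 80.6 (ablation) and 70.6 (drug), SD 19.8 in both groups, two-sided alpha 0.05, power 0.80, dropout 20%.

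- Difference: 80.6 − 70.6 = 10. Standardised difference: 10/19.8 = 0.505.
- Power for n per group is P(|T| > t(0.975; 2n − 2)), where T is noncentral t with noncentrality 10 / (19.8 × √(2/n)).
- n = 62: noncentrality 2.812, 122 degrees of freedom, power 0.797.
- n = 63: noncentrality 2.835, 124 degrees of freedom, power 0.80306, which is the value printed in section 3.1.
- So 63 is the smallest n per group that reaches 0.80.
- Dropout: 63 / (1 − 0.20) = 78.75, rounded up to 79 per group.
- Total: 2 × 79 = 158, the Summary's sample size.

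The two-group calculation accounts for all 158 patients. The only 0.80 in it is the power, which has nothing to do with the 80% target.

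**Step 3. Look for a responder definition that would rescue the 80%.** Section 3.1 mentions AFEQT improvements of 5, 10 and 15 points, taken from a cited cohort study that graded improvement and compared rates. The protocol uses these steps only to set the assumed drug-group mean (75.6, 70.6 or 65.6). It does not use them to define a responder in this study.

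**The case against.** The strongest reply is that one Summary sentence stands against a consistent body of text, so the intent is clear. Section 3.1 gives the AFEQT hypotheses, the sidedness and alpha, and the purpose and objective state the comparison. That stands as evidence of intent, and it shows which of the two criteria should survive. It does not remove the other, which is current text.

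A second reply is that the term main evaluation indicators is undefined and plural, and that 80% was probably meant for the recurrence-free rate. This is plausible, since that endpoint is described as a success rate. But the text does not say so, and that endpoint is secondary. On this reading a secondary, PFA-only rate has been labelled as the main indicator.

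Some stronger readings are tempting but not supported:

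- A reader might infer that the protocol has no primary two-group comparison, because section 9 names no AFEQT test. Section 3.1 does give the hypotheses and alpha, and the named test may sit in a statistical analysis plan that is not shown.
- A reader might infer that adverse events, where an exact "method was used to compare the two groups of adverse events", are the only comparison in the Summary's analysis text. The same text also lists a comparison of the total dropout rate.
- A reader might infer that 80% could never be applied to AFEQT. It is undefined as written; an added responder definition would make it computable.
- A reader might infer that the study is underpowered for a test against 80%. The documents give no expected rate and no test for that comparison, so they support no power figure.

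**Conclusion.** The stated criterion is wrong as written. The 80% target is undefined for the primary endpoint and contradicts the purpose, objective, groups and sample size, none of which uses it. The protocol therefore has two incompatible main success criteria.

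The numerical effect on the design is nil: N stays at 63 per group evaluable, 79 per group enrolled and 158 in total. The defect lies in the decision rule. The conclusion rests on reading the main evaluation indicator as the primary endpoint. If it means secondary endpoint (1) instead, the label is wrong and the same passage still needs correcting.

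A reader might also infer that the repair must bring section 3.1, which works with 12-month means, into line with section 5.1, which defines change from baseline and calls higher scores worse. That is a separate issue and more than wording: the SD of 19.8 belongs to 12-month scores, and the protocol gives no SD of change for that cohort. This point does not depend on it.

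**What to change.** Delete the benchmark and 80% sentences from the Summary's Statistical analysis row. Replace them with the comparison the study is sized for: the PFA-versus-drug difference in the primary AFEQT endpoint, null hypothesis of no difference, two-sided alpha 0.05.

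If the sponsor wishes to keep 80%, tie it by name to secondary endpoint (1), the PFA recurrence-free rate, and mark it as descriptive or supportive so that it cannot decide the main conclusion. Justify the benchmark as well, because it comes from drug-refractory AF whereas exclusion (2) removes prior class I/III users apart from under 7 days' use.

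The cost is protocol wording only. Sample size, design and data collection do not change.

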1、 The AFEQT value of the endpoint of the pulse catheter ablation group be selected from the

CABANA heart failure cohort at 12 months, which is 80.6 (19.8). Referring to the KiCS-AF cohort study, which divided the AFEQT improvement value into three levels of 5, 10 and 15, we set the AFEQT value of the drug treatment group to 75.6/70.6/65.6.

2、 Set the AFEQT of the drug group to 75.6, $\alpha=0.05$, $\beta=0.2$, and 248 patients are required in each group.

Numeric Results for an Unequal-Variance T-Test

$$\delta = \mu_1 - \mu_2$$

Hypotheses: $H_0: \delta = 0$ vs. $H_1: \delta \neq 0$

Target Power	Actual Power	N1	N2	N	μ_1	μ_2	δ	σ_1	σ_2	Alpha
0.8	0.80138	248	248	496	80.6	75.6	5	19.8	19.8	0.05

3、 Set the AFEQT of the drug group to 70.6, $\alpha=0.05$, $\beta=0.2$, and 63 cases are needed in each group. Considering a dropout rate of 20%, 79 cases are needed in each group.

Numeric Results for an Unequal-Variance T-Test

$$\delta = \mu_1 - \mu_2$$

Hypotheses: $H_0: \delta = 0$ vs. $H_1: \delta \neq 0$

Target Power	Actual Power	N1	N2	N	μ_1	μ_2	δ	σ_1	σ_2	Alpha
0.8	0.80306	63	63	126	80.6	70.6	10	19.8	19.8	0.05

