(4) The occurrence of other adverse events and serious adverse events: Observe and record them throughout the trial. Serious adverse events should be tracked until the problem is resolved or the investigator determines that it has become "chronic" or "stable" or "sufficient to explain this abnormality". Reports of these adverse events should be recorded.

7. Safety evaluation

Safety refers to the absence of pulmonary vein stenosis, cardiac tamponade, phrenic nerve injury, esophageal injury, and femoral artery and vein injury, thrombosis/air embolism, myocardial infarction, stroke, TIA, asymptomatic cerebral infarction, coronary artery spasm, vagal reflex with severe bradycardia and other surgical complications during the perioperative period.

8. Time of participation in the study (each participation time and total time)

The time of participation in the study is the time when patients with persistent atrial fibrillation and HFpEF are planned to receive drug treatment or pulsed field ablation surgery, that is, the time of enrollment. The follow-up time is 1 month, 3 months, 6 months, and 12 months after enrollment. The total time is 12 months after the start of treatment. .

9. Data management and statistical analysis plan, data confidentiality plan

(1) The research data are managed and stored in the cardiology laboratory by full-time scientific research personnel.

(2) Data statistics and analysis

1. Statistical processing: SPSS22.0 statistical software was used for statistical analysis.
2. Normally distributed quantitative data, such as troponin, liver and kidney function, blood lipids, height, weight, EF, e/e', proBNP, etc.
3. Non-normally distributed quantitative data, such as age, are described as median ± interquartile range.
4. A t-test is planned for the results of molecular experimental data;
5. The composition ratio is used for statistical description of qualitative data, and the chi-square test is used for statistical inference. Cardiac function (NYHA classification) is tested using the K-W rank sum test;
6. $P < 0.05$ is considered significant.

10. Confidentiality Plan

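### The one test named for adverse events compares two groups, but the safety question is the complication rate after ablation, for which no interval is planned

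*Protocol*

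**What the plan says.** The Protocol deals with the analysis of safety in three places.

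- **Study Protocol Summary, Statistical analysis, item 2.** Description comes first: "List the number and frequency of all adverse events, as well as the incidence of adverse events and serious adverse events". One comparison follows, in a sentence split by a table break: "The exact probability" "method was used to compare the two groups of adverse events".
- **Section 9, part (2).** Item 5 says that for qualitative data "the chi-square test is used for statistical inference", with no exception for adverse events. Item 6 sets the significance level at 0.05 for all tests. Neither item gives the sidedness of the adverse-event test.
- **Sections 2.2 and 7.** The first item of research content is to observe the perioperative safety of the ablation procedure. Section 7 defines safety as the absence of a list of perioperative surgical complications, such as tamponade, pulmonary vein stenosis, and phrenic nerve, esophageal and femoral vessel injury.

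Section 1 gives two reference rates. For thermal energy, "the complication rate of radiofrequency or cryocatheter ablation is approximately 2.9% to 10" per cent. For the study device, from its global key study, "the incidence of unsafe events for the product submitted this time was 0.7" per cent. The Protocol sets neither as a safety limit for this trial. It states no confidence interval, margin or acceptable rate for safety. The 80% target in the summary belongs to the main evaluation indicator, and the sample size in Section 3.1 rests on AFEQT alone.

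**The concern.** The named test and the stated safety question do not match. The question in Sections 2.2 and 7 is how often ablated patients have a procedural complication. The drug group has no ablation, so for most of the listed events its count is zero by design. The P value then mainly reflects how many events it takes to differ from zero. If all adverse events are pooled instead, drug side effects in one group can offset procedural complications in the other.

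With sparse events and 79 per group, non-significance is the likely result over much of the range of rates that the Protocol itself quotes. The planned incidences are point estimates with no statement of precision. A report could therefore follow the plan exactly, present no significant difference or zero complications, and give no indication of how high the true rate could be.

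The two named tests can also disagree on the same data, so the result may depend on which section the analyst follows.

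**Working it through.** **Inputs.** Group size 79, or 63 after the assumed dropout (Section 3.1). Level 0.05 (Section 9). Reference rates 0.7%, 2.9% and 10% (Section 1). Two assumptions are added: the exact test is Fisher's and two-sided, and for power the drug-group rate of these events is 0%, with 0.7% as an alternative.

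**The plan's own figure.** The chosen scenario reads "Set the AFEQT of the drug group to 70.6, $\alpha=0.05$, $\beta=0.2$, and 63 cases are needed in each group". A noncentral t calculation with difference 10 and SD 19.8 gives power 0.797 at 62 and 0.803 at 63 per group. Then 63 / (1 − 0.20) = 78.75, rounded up to 79. Both figures reproduce.

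**Fisher test, 79 versus 79.** With all k events in one group, the one-sided p is C(79,k) / C(158,k). By symmetry the two-sided p is twice that.

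- k = 5: (79·78·77·76·75) / (158·157·156·155·154) = 0.0293; two-sided 0.0586.
- k = 6: 0.0293 × 74/153 = 0.0142; two-sided 0.0283.
- 7 versus 1 gives 0.0634 two-sided; 8 versus 1 gives 0.0338.

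So 6 versus 0 is the smallest split against zero that reaches 0.05 two-sided. With 63 per group the results are similar: 5 versus 0 gives 0.0576 and 6 versus 0 gives 0.0276.

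**Chi-square for the same 5 versus 0.**

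- Uncorrected: 158 × (5 × 79)² / (79 × 79 × 5 × 153) = 3950/765 = 5.16, p = 0.023.
- With continuity correction: 158 × (395 − 79)² / (79 × 79 × 5 × 153) = 3.30, p = 0.069.

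The expected event count is 2.5 per group, so an exact test is the usual choice here.

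| Reading of 5 versus 0 at 79 per group | p |
|---|---|
| Fisher, two-sided | 0.059 |
| Fisher, one-sided | 0.029 |
| Chi-square, uncorrected | 0.023 |
| Chi-square, corrected | 0.069 |

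**Power of the two-sided Fisher test, 79 per group.** With a drug-group rate of 0%, this is P(X ≥ 6) for X binomial (79, rate).

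| True ablation rate | Drug rate 0% | Drug rate 0.7% |
|---|---|---|
| 0.7% | about 0% | about 0% |
| 2.9% | 3% | 2% |
| 6.3% | 38% | 26% |
| 10% | 81% | 67% |

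**Exact (Clopper-Pearson) intervals for the ablation group.**

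- 0/79: 95% upper limit 1 − 0.025^(1/79) = 4.6%. The one-sided 95% limit is 1 − 0.05^(1/79) = 3.7%. Both exceed 2.9%. For 0/63 the two-sided upper limit is 5.7%.
- 5/79 = 6.3%: 95% interval 2.1% to 14.2%. The estimate is nine times 0.7% (6.3/0.7 = 9), and the lower limit lies above 0.7%. The two-sided Fisher test would still call 5 versus 0 not significant.

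**The case against.** The strongest reply is that the Protocol does not commit the error feared. A reader might infer that the safety claim will rest on a non-significant test, but no passage says so. The title names a topic, Section 2.2 sets out to observe safety, incidences are listed before any test, and Section 7 defines safety by the absence of complications, not by a P value. This stands: misuse is left open by the plan, not prescribed.

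A reader might also infer that the exact test is the only inference available. That is not so, because item 5 of Section 9 covers qualitative data in general. Nor is the 0.059 fixed by the text: the two-sided hypotheses in Section 3.1 are for AFEQT, and a one-sided Fisher test gives 0.029. Both corrections stand. They also show that the result for 5 versus 0 depends on an unresolved choice.

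A comparison with drug treatment has its place, since Section 2.1 sets out to evaluate efficacy and safety through differences between the two treatments. Over 12 months the drug group will have adverse events of its own, so 5 versus 0 illustrates procedural complications, not all adverse events. This is a reason to keep the test as supplementary.

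Finally, interval methods are often left to a statistical analysis plan, which is not shown, and low power for rare events is normal at this size. Absence of an interval alone would therefore be no finding. What remains is that the Protocol itself fixes a test that does not match its definition of safety, and names a different test elsewhere.

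**Conclusion.** The point holds in a limited form. The exact test is the only test named specifically for adverse events. It does not answer the safety question of Sections 2.2 and 7, and it conflicts with the general chi-square rule in Section 9. Assuming a two-sided test and 79 per group, 5 versus 0 is not significant (p = 0.059). With no such events in the drug group, the chance of significance is about 3% at a true rate of 2.9% and 38% at 6.3%. The limit for zero events does not depend on the choice of test: 0 of 79 leaves rates up to 4.6% possible, above the lower end quoted for thermal ablation. That rate and the 0.7% serve here only as yardsticks, since the Protocol adopts neither as a benchmark.

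The documents do not support the claim that safety will be concluded from non-significance. They only leave room for it. Safety is a secondary endpoint, and the AFEQT sample size is unaffected, so this is an inexpensive improvement and not a flaw in the design.

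**What to change.** 1. Make the main safety result the proportion of ablated patients with at least one procedure-related complication from the Section 7 list, with a Clopper-Pearson 95% confidence interval. Base the safety conclusion on the upper limit.
2. Report the difference between groups in the proportion of patients with at least one serious adverse event, with a 95% confidence interval.
3. Keep the exact test as a supplementary comparison and state that it is two-sided.
4. Reconcile the summary with Section 9, item 5, so that one test applies to adverse events.

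The cost is a few lines of analysis text, with no extra patients or data. The downside is a less favourable safety statement: even with no complications, the report would have to say that rates up to about 4.6% cannot be excluded.
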